3.4.1 Study Observations Table Detailed Description

Hill-Rom®	Evaluation of a practice change to include The MetaNeb® System to reduce postoperative pulmonary complications			Page 20 of 31
	CBI	8 September 2016	Rev C	Protocol #: CR-RR2015- 001

Documentation of observations will be completed by study staff based on review of the patient's medical records. A detailed description of documentation requirements for each parameter is below.

Demographic Data: The following data will be recorded from the patient medical record: Age, Height, Weight, Race, Gender, ASA score, Documented obesity and/or $BMI \geq 30 \text{ kg m}^2$.

Medical History: Pulmonary history will be recorded from the patient medical record including: Asthma, Cystic Fibrosis, Bronchiectasis, COPD, Neuromuscular Disease, Other Pulmonary Condition(s), Obstructive Sleep Apnea

Pre-surgery Respiratory Status: Pre-surgery respiratory status such as Invasive Mechanical Ventilation, Non-invasive Mechanical Ventilation, CPAP, Supplemental oxygen will be recorded.

Post-Surgery Data (day 0): Following surgery, the albumin level (if available in the medical record) and surgery type will be recorded.

Location: The post-surgery location of each patient upon return to the hospital unit or floor (ICU, General Care, etc.) will be recorded. The patient's location during the first seven days, or until the time of discharge from the hospital, whichever occurs first, will also be recorded at regular intervals based on entries in the medical record.

Respiratory Status: The respiratory status of each patient, following surgery will be recorded. Respiratory status during the first seven days, or until the time of discharge from the hospital, whichever occurs first, will also be recorded at regular intervals based on entries in the medical record. Respiratory status will include documentation of the mode of support, the device in use and the settings.

Respiratory Milestones: Key respiratory milestones that occur each day will be recorded based on entries in the medical record. These include 1) extubation, 2) re-intubation, 3) return to baseline respiratory support, 4) Diagnosis of Pneumonia and 5) Readmission to the ICU or an elevated level of care. These milestones will be recorded for each day until discharge from the hospital, or through day seven (7) following the day of surgery, whichever occurs first.

Respiratory Treatments: Standard respiratory treatments including CPAP therapy (non-continuous), IPPB, Nebulizer treatments, Chest physiotherapy, and others will be

Hill-Rom®	Evaluation of a practice change to include The MetaNeb® System to reduce postoperative pulmonary complications			Page 21 of 31
	CBI	8 September 2016	Rev C	Protocol #: CR-RR2015-001

recorded for each day until discharge from the hospital, or through day seven (7) following the day of surgery, whichever occurs first. Type of therapy and the number of treatments received on each day will be recorded.

During Stage II, each MetaNeb® therapy will be documented including time and duration of therapy and adherence to defined treatment regimen

Hospital Discharge Summary: A summary including date and time of discharge along with the location to which the patient is being discharged will be completed after discharge.

ICU Admission/Discharge Summary (Day 8 – Discharge): Dates and times of all ICU admissions, or admissions to a unit for an elevated level of care, along with discharges from those units, that occur between post-surgery day 8 and discharge from the hospital, will be documented.

Discharge Respiratory Summary (Day 8 – Discharge): Dates and times of each initiation and discontinuation of mechanical ventilation that occur between post-surgery day 8 and discharge from the hospital, will be documented.

30-day Readmission: Hospital medical records for each patient will be evaluated after 30 days post discharge, to determine if any hospital readmissions had occurred.

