1.0 Introduction

1.1 Background and Significance

Post-operative pulmonary complications (PPC) are associated with significant excess morbidity, mortality and healthcare expenditure. The incidence of “important” PPCs, across all surgeries, is approximately 2-5% in the general surgical population. There are factors, however, that place certain patients, and patients with certain procedures, at considerably higher risk for PPCs. One of the key factors in development of PPCs is the type of surgery. Following upper abdominal and thoracic surgery, pulmonary complications are the most common surgical complications. Other risk factors include advanced age, American Society of Anesthesiologists (ASA) physical status classification score ≥ 2 , functional dependency, congestive heart failure and chronic obstructive pulmonary disease. Of these, ASA score ≥ 2 and functional dependency have consistently been associated with a higher rate of significant PPCs such as post-operative respiratory failure (PRF). PRF requiring prolonged mechanical ventilation (MV) or re-intubation accounts for the majority of poor outcomes and high economic costs.^[1-4] Other risk factors that have been associated with increased risk of PPCs include history of COPD, smoking history and BMI $\geq 30 \text{ kg/m}^2$.^[1-5]

Although PPCs are an incompletely understood multifactorial syndrome, atelectasis is recognized as a critical component.^[6] Evidence has shown that atelectasis is a common precursor and concomitant feature of PPCs. Nearly all patients undergoing major surgery experience some degree of transitory, clinically unimportant atelectasis, most of these patients do not require aggressive therapy. There is, however, a more urgent need to treat atelectasis in subpopulations of high-risk individuals, in order to prevent more serious complications including progression to PRF.^[7]

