3.2 Study Population

The study population consists of adult post-surgical patients who have undergone thoracic, aortic or upper abdominal surgery who are at high risk for PPCs.

3.2.1 Inclusion Criteria:

Patients who meet all of the following criteria will be included in the study:

- Age \geq 18 years
- Post-thoracic, -upper abdominal or -aortic surgery
- Open surgical procedure
- Incision at or above the umbilicus
- High risk defined by:
 - Documented ASA class \geq 3

Hill-Rom®	Evaluation of a practice change to include The MetaNeb® System to reduce postoperative pulmonary complications			Page 16 of 31
	CBI	8 September 2016	Rev C	Protocol #: CR-RR2015- 001

OR

- Documented ASA class 2 **AND** One or more of the following:
 - Current Smoker or Smoking history within past 6 months
 - History of COPD
 - Documented Obesity and/or BMI $\geq 30 \text{ kg/m}^2$
 - Age ≥ 75

3.2.2 Exclusion Criteria:

Patients who meet any of the following criteria will be excluded (or will be exited) from the study:

- Contraindication to Continuous High Frequency Oscillation (CHFO) therapy (e.g. untreated tension pneumothorax)
- Minimally invasive or “...scopic” surgical procedure
- Spinal surgery involving a posterior approach
- Surgery for organ transplant
- Chronic invasive Positive Pressure Ventilation (PPV) therapy

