3.4 Study Observations Table

The study observations and documentation timeline is outlined in Table 1.

Table 1. Study Observations Table

Day	Pre-Surgery	Day of Surgery	Post Surgery Day 1 - Day 7	Hospital Discharge	Early Term	Day 30 Post Discharge
Selection Criteria / Enrollment	X					
Informed Consent *	X					
Demographic Data	X					
Medical History	X					
Pre-Surgery Respiratory Status (Patient's Baseline)	X					
Post-Surgical Data (day 0) at day of surgery.		X				
Location (7A & 7P)		X	X			
Respiratory Status (Each Shift)		X	X			
Respiratory Milestones		X	X			
Respiratory Treatments		X	X			
Hospital Discharge Summary				X		
ICU Admission/Discharge Summary (Day 8 - Discharge)				X		
Discharge Respiratory Summary (Day 8 - Discharge)				X		
30-day Readmission					X	
Study Exit Form				X	X	

* Informed consent will be obtained only for subjects in Stage II.

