### **6.1.5 Medical History**

The pulmonary status will be tabulated, including the presence/absence of asthma, cystic fibrosis, bronchiectasis, COPD, neuromuscular disease, obstructive sleep apnea, other pulmonary conditions.

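### Smoking is a stated PPC risk factor and an eligibility qualifier, but the plan does not require it to be recorded for all patients, so its balance between stages may not be shown or adjusted for

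*Protocol*

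**What the plan says.** Protocol 1.1, after its first list of risk factors, adds: "Other risk factors that have been associated with increased risk of PPCs include history of COPD, smoking history and BMI" of 30 or more.

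Protocol 3.2.1 offers two routes to high-risk status. ASA class 3 or above is sufficient alone. The other route reads "Documented ASA class 2 AND One or more of the following", and the four options are "Current Smoker or Smoking history within past 6 months", COPD, obesity or BMI of at least 30, and age of at least 75.

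Protocol 3.4.1 sets out what is recorded. The demographic items are "Age, Height, Weight, Race, Gender, ASA score, Documented obesity" and/or BMI of at least 30. The medical-history items are "Asthma, Cystic Fibrosis, Bronchiectasis, COPD, Neuromuscular Disease, Other Pulmonary Condition(s), Obstructive Sleep Apnea". Surgery type is recorded after the operation. Table 1 in Protocol 3.4 also has a row called "Selection Criteria / Enrollment", whose content 3.4.1 does not describe.

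SAP 6.1.3 summarises age, gender, race, ASA score, height, weight, BMI and obesity by stage. SAP 6.1.5 tabulates "asthma, cystic fibrosis, bronchiectasis, COPD, neuromuscular disease, obstructive sleep apnea, other pulmonary conditions". Neither mentions smoking.

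Protocol 3.5.2 says the stages will be compared to find associations attributable to the device. SAP 6.3 gives the PPC proportion with a 95% confidence interval and names no covariate.

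**The concern.** The four ASA 2 qualifiers are factors that the sponsor itself regards as marking high risk. Three of them reach the data list and the baseline tables. Smoking does not, and no reason is given.

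The design gives no protection by randomisation, so the baseline tables by stage are the reader's main evidence that the two groups are alike. The groups are also assembled differently. Stage I is a random sample of charts, with a consent waiver to be requested (Protocol 3.1.2 and 5.1). Stage II patients must give consent, and those who did not receive the device are dropped from the primary population (Protocol 5.1, SAP 6.2). Consent and receipt of treatment could plausibly be related to smoking. If the smoking mix differs between stages, part of the Stage II versus Stage I difference in PPC reflects that mix and would be read as a device effect.

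**Working it through.** **Step 1: the four ASA 2 qualifiers against the data lists.**

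| Qualifier (Protocol 3.2.1) | Named in Protocol 3.4.1 | Named in SAP 6.1.3 or 6.1.5 |
|---|---|---|
| COPD | yes | yes (6.1.5) |
| Obesity or BMI ≥ 30 | yes | yes (6.1.3) |
| Age ≥ 75 | yes, as age | yes, as age (6.1.3) |
| Smoking | no | no |

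**Step 2: could the selection form fill the gap?** A form that records every criterion for every patient would. A form that records only what is needed to establish eligibility would not: an ASA 3 patient needs no smoking entry, and an ASA 2 patient who qualifies on COPD, obesity or age needs none either. The documents do not say which kind of form it is. If smoking is recorded only where needed, its missingness follows ASA class, which Protocol 1.1 also treats as a risk factor.

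**Step 3: how large could the bias be?** The documents give no smoking prevalence and no smoking risk ratio, so both are assumptions here. Let RR be the smoking risk ratio for PPC, and p1 and p2 the proportions of smokers in Stages I and II. With no true device effect and the same RR in both stages,

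spurious risk ratio = [1 + (RR − 1)p2] / [1 + (RR − 1)p1].

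| RR | p1 to p2 | Spurious risk ratio | Relative reduction | Points at 10% PPC |
|---|---|---|---|---|
| 1.5 | 30% to 20% | 1.10/1.15 = 0.957 | 4.3% | 0.43 |
| 2 | 30% to 20% | 1.20/1.30 = 0.923 | 7.7% | 0.77 |
| 1.5 | 40% to 25% | 1.125/1.20 = 0.9375 | 6.3% | 0.63 |
| 2 | 40% to 25% | 1.25/1.40 = 0.893 | 10.7% | 1.07 |

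A second set of assumptions (p2 = 20%, p1 from 25% to 35%, RR from 1.5 to 2.5) gives spurious risk ratios from 0.98 to 0.85. A rise in smokers would bias the comparison the other way and hide a benefit.

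**Step 4: scale.** The 10% rate is the middle of the 5% to 15% range in Protocol 3.5.1, and each stage has about 200 patients. With 10% in both stages, the 95% half-width for the difference is 1.96 × √(2 × 0.10 × 0.90 / 200) = 1.96 × 0.030 = 5.9 points. The spurious difference of 0.4 to 1.1 points is small beside it.

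**Step 5: would chance alone shift the smoking mix that far?** With 25% smokers (assumed) in both stages, the 95% range for a chance difference in prevalence is ±1.96 × √(2 × 0.25 × 0.75 / 200) = ±8.5 points. A 10-point fall is slightly beyond this and a 15-point fall well beyond it, so the tabulated scenarios mostly need a systematic shift.

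**The case against.** Five objections carry weight.

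- **Smoking may in fact be collected.** A reader might infer that it will be missing for every patient who qualifies on ASA class alone. The documents do not support that. The content of the selection row is not described, no case report form is included, and both medical-history lists are introduced with an open-ended word. What stands is that nothing requires smoking to be recorded for everyone.
- **Eligibility can be checked.** A reader might infer that the eligibility of ASA 2 smokers cannot be verified. Both stages work from medical records, so it can be. The gap concerns balance across the whole sample.
- **The SAP adjusts for nothing.** ASA score, age, BMI and COPD are collected but enter no model. Under SAP 6.3 as it stands, a smoking field would add a table row and leave the estimate unchanged. This stands, and the fix has to deal with it.
- **Smoking is not the only omission.** Protocol 1.1 also names functional dependency and congestive heart failure, and gives functional dependency more prominence. Neither is listed in 3.4.1. This stands. What distinguishes smoking is that it is also an eligibility qualifier.
- **The bias is small and its inputs are assumed.** The documents give no direct reason to expect a large shift at the same sites in adjacent periods, and recorded COPD and ASA score may capture part of any imbalance. This stands and limits the severity. The different assembly of the two stages still makes a shift plausible enough to look for.

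**Conclusion.** The point holds in limited form. Smoking is the only one of the four ASA 2 qualifiers not named in the recorded data or the SAP tables. Following the plan as written does not ensure that its balance between stages can be shown or adjusted for.

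Under the assumed risk ratios and prevalences in the first table of scenarios, the effect on the comparison is a 4% to 11% spurious relative reduction, well inside sampling error at about 200 per stage. A reader might infer that smoking imbalance could by itself produce an apparent device benefit of important size; these figures do not support that. This is a minor weakness and a cheap improvement.

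**What to change.** 1. In Protocol 3.4.1, add smoking status as a chart-abstracted item for all patients in both stages: current, within the past 6 months, neither, or not documented.
2. Tabulate it by stage in SAP 6.1.3 or 6.1.5. Show the not-documented count for each stage and do not fold it into the non-smokers.
3. In SAP 6.3, pre-specify a covariate-adjusted Stage II versus Stage I comparison of PPC that includes smoking together with ASA score, age, BMI, COPD and surgery type, all of which are already collected. At a 10% PPC rate, 400 patients give about 400 × 0.10 = 40 events, so code the covariates sparingly and fix them before the stages are compared.
4. Abstract functional dependency and congestive heart failure in the same way where they are charted.

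The cost is a little extra abstraction from records that are already being opened, one table row per item, and one added analysis. No new visit or procedure is needed. Some Stage I charts may lack the smoking entry, and that limitation should be reported.

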Pre-surgery data will be collected for eligible patients in both stages. In both Stage I and Stage II, outcomes will be tracked for each day from the time of the post-surgical admission to the hospital unit through post-surgery day seven (7). Additionally, hospital length of stay (LOS) and total ICU LOS will be determined based on documentation of admission and discharge dates and times for all days of hospitalization. Length of time on mechanical ventilation (LOMV) will be determined based on documentation of initiation and discontinuation dates and times for all days

Hill-Rom®	Evaluation of a practice change to include The MetaNeb® System to reduce postoperative pulmonary complications	Page 14 of 31
CBI	8 September 2016	Rev C Protocol #: CR-RR2015-001

of hospitalization. LOS and LOMV data will be collected from the medical record upon discharge from the hospital. Hospital records will also be reviewed after 30 days to determine if readmission to the hospital occurred for any study patients.

A timeline showing data procedures and collection points is included as Table 1 Study Observations Table.

The estimated study enrollment is 200 patients in both stages. However, an adjustment in sample size may be made based on the incidence rate for post-operative pulmonary complications in Stage I, to allow for a robust estimate and assessment of the effect of therapy with The MetaNeb® System.

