3.3 Evaluation Criteria/Effectiveness

The CHANGE IN PRACTICE therapy regimen (which includes therapy with The MetaNeb® System) will be evaluated to determine if there is a decrease in the number of patients who experience Significant Postoperative Pulmonary Complications among the group of patients treated with The MetaNeb® System. Endpoints are described below:

Primary Endpoint:

Significant Postoperative Pulmonary Complication (PPC):

One or more of the following that occurs within seven (7) days of the post-surgical admission will be considered a Significant Postoperative Pulmonary Complication (PPC)

- **Patient Requires Prolonged Mechanical Ventilation:**

Defined as patient requirement for invasive mechanical ventilation (MV) for > 24 hours (after hour 24) post-operatively. This includes patients that require re-intubation and MV after hour 24, regardless of length of time on MV in the first 24 hours postoperatively.

Hill-Rom®	Evaluation of a practice change to include The MetaNeb® System to reduce postoperative pulmonary complications	Page 17 of 31
CBI	8 September 2016	Rev C Protocol #: CR-RR2015-001

- **Patient requires prolonged respiratory support for > 24 hours from post-surgical admission**
 - Requirement for non-invasive ventilation (NIV) above patient's baseline requirement after hour 24, or continuous positive airway pressure (CPAP) above patient's baseline requirement after hour 24.
 - Requirement for O₂ therapy > 40 % FiO₂ or > 5 LPM via NC (and above patient's baseline) after hour 24 postoperatively.
- **Diagnosis of Pneumonia Within Seven (7) Days**
 - Physician documented pneumonia AND
 - Radiologists report indicating pneumonia / new or expanded infiltrate AND
 - Elevated or low Temperature (> 38° C or < 36° C, or as defined by the site) and/or elevated white count above the upper level of normal as defined by the site
- **Readmission to ICU (or transfer to an elevated level of care) for pulmonary complications within seven (7) days of the post-surgical hospital admission**

Defined as readmission to the ICU within seven days of post-surgical hospital admission or readmission to an elevated care unit such as special care or ICU step-down unit after being moved to a lower (e.g. general care) floor (e.g. patient discharged from ICU on day 4 at 0800 is readmitted to the ICU before day 8 at 0800).

Secondary Endpoints:

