### **6.3 Analysis Methods – Primary and Secondary Endpoints**

#### **Primary Endpoint— Proportion of subjects who have a postoperative pulmonary complication**

The proportion of subjects who have a PPC within 7 days of post-surgery hospital admission will be presented with 95% confidence intervals.

Incidence of each of the 4 components that contribute to the primary endpoints, will also be presented.

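### The primary endpoint is defined over 7 days but its data are recorded only to discharge, so a qualifying event after early discharge would be scored as no PPC

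*Protocol*

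**What the plan says.** **The endpoint has a fixed window.** Protocol 3.3 counts "One or more of the following that occurs within seven (7) days of the post-surgical admission". SAP 2.1 repeats the 7 days, and SAP 6.3 states: "The proportion of subjects who have a PPC within 7 days of post-surgery hospital admission will be presented with 95% confidence intervals". SAP 6.1.1 truncates ventilation stop times at 7 days after post-surgical hospital admission (PSHA), not at discharge.

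**The recording does not.** Protocol 3.4.1 lists the milestones (extubation, re-intubation, return to baseline support, pneumonia, readmission to ICU or elevated care) and adds: "These milestones will be recorded for each day until discharge from the hospital, or through day seven (7) following the day of surgery, whichever occurs" sooner. The same section limits the data behind the support component: "Respiratory status during the first seven days, or until the time of discharge from the hospital, whichever occurs first". Patient location is limited in the same way.

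**One section has no discharge cut-off.** Protocol 3.1.2 says that in both stages "outcomes will be tracked for each day from the time of the post-surgical admission to the hospital unit through post-surgery day seven (7").

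**After discharge there is one data source.** Protocol 3.4.1 says: "Hospital medical records for each patient will be evaluated after 30 days post discharge, to determine if any hospital readmissions had occurred". Protocol 3.3 and SAP 2.2 make this an any-cause secondary endpoint. SAP 2.2 (hospital length of stay) also plans admission and discharge times for every hospital admission, so readmission dates should exist. Nothing asks whether pneumonia, ventilation, respiratory support or ICU care occurred during the readmission, and nothing in SAP 6.1.1 passes a readmission to the PPC flags.

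**The concern.** Take a patient who goes home on day 4 and is readmitted on day 6 with pneumonia meeting all the criteria. Protocol 3.3 calls this a PPC. Under Protocol 3.4.1 milestone recording stopped on day 4, so no milestone exists. SAP 6.1.1 has no rule for patients discharged before day 7, and flags 1 and 2 default to zero. With no event recorded, the patient would be counted as event-free for days nobody looked at.

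Two things are at stake. First, observation time depends on length of stay, which is itself a secondary endpoint and could differ between two successive, non-randomized periods. A difference in early discharge could then appear as a difference in PPC. Second, Stage I exists to estimate incidence, and Protocol 3.1.2 and SAP 1 allow that estimate to drive a sample-size adjustment. An undercount there matters even if both stages are affected equally.

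**Working it through.** **Is there another route into the endpoint?** The Day 8-to-discharge summaries cover only patients still in hospital. The 30-day review yields the fact of readmission and, through SAP 2.2, its dates. Neither carries the pneumonia criteria, ventilation, support level or ICU care. So no planned data item captures a qualifying event between an early discharge and day 7.

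**Which components are exposed?** Mainly pneumonia, and ventilation or support that starts on a readmission. Support continuing past hour 24 is mostly seen before discharge. For the ICU component the text is unclear: Protocol 3.3 illustrates it as a return to higher care after a move to a lower floor, which can be read as within the initial stay.

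**Size.** The plan gives no figure to reproduce.

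- From the documents: n = 200 per stage; expected PPC incidence p of 5% to 15% (Protocol 3.5.1); two-sided 5% tests (SAP 6).
- Assumed, because the documents give neither: e, the share discharged before day 7, and r, the risk among them of a first PPC between discharge and day 7.
- Missed events per stage = 200 × e × r.
- Observed rate = p − e × r.
- False difference with no true effect and equal r = r × (e2 − e1).

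| e1 vs e2 | r | Missed per 200 | False difference (points) |
|---|---|---|---|
| 30% vs 50% | 0.5% | 0.3 vs 0.5 | 0.1 |
| 30% vs 50% | 3% | 1.8 vs 3.0 | 0.6 |
| 50% vs 60% | 2% | 2.0 vs 2.4 | 0.2 |
| 50% vs 60% | 5% | 5.0 vs 6.0 | 0.5 |
| 20% vs 60% (extreme) | 3% | 1.2 vs 3.6 | 1.2 |

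Pairing the ends of the 30-60% range with r = 5% would give 0.05 × 0.30 = 1.5 points.

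**Against sampling error.** The 95% half-width for a between-stage difference is 1.96 × √(2p(1 − p)/200), which is 4.3 points at p = 5% and 7.0 points at p = 15%. Every false difference above is smaller.

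**Effect on a simple two-proportion comparison** (normal approximation, unpooled standard error, no true effect; SAP 6.3 names no between-stage test):

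- p = 15%, 30% vs 50%, r = 3%: observed 14.1% vs 13.5%, ratio 0.957, type I error 0.054.
- p = 5%, same inputs: observed 4.1% vs 3.5%, ratio 0.854, type I error 0.061.
- p = 5%, 20% vs 60%, r = 3%: observed 4.4% vs 3.2%, ratio 0.727, type I error 0.096.

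**Does the direction always hold?** No. With e = 30% and r = 3%, 200 × 0.30 × 0.03 = 1.8 events are missed; with e = 40% and r = 2%, 200 × 0.40 × 0.02 = 1.6. The stage with more early discharges misses fewer.

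**The case against.** The best defence is that in-hospital ascertainment to day 7 is a workable choice for a chart-review study, that the same rule applies to both stages, and that length of stay is reported, so a large imbalance would show. The likely bias is about one patient per 200, and one clarifying sentence might settle the wording. The points about size and workability stand. They do not remove the mismatch: the primary definition carries no inpatient limit, although the authors write one where they want it, as in the secondary ICU-readmission endpoint (Protocol 3.3; SAP 2.2 and 6.3). Mean or median length of stay also does not show the share discharged before day 7.

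A reader might go further in four ways that the documents do not support.

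- That the 30-day review records only whether a readmission occurred. SAP 2.2 plans times for each hospital admission; the clinical content is what is missing.
- That the stage with shorter stays always loses more events. This needs similar post-discharge risk and a larger share leaving before day 7; a difference in stay arising after day 7 has no effect.
- That both rates are understated relative to the 5-15% in Protocol 3.5.1. The protocol does not say whether those published rates are in-hospital.
- That every component is equally exposed. The ICU component may already be confined to the initial stay.

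**Conclusion.** The inconsistency is real. Followed as written, Protocol 3.4.1 delivers in-hospital PPC to discharge or day 7, while Protocol 3.3 and SAP 6.3 report it as 7-day PPC. That an early-discharged patient would be scored as no PPC is an inference from the absence of any rule or data item to the contrary, but it is the natural outcome of the derivation.

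The size is unknown, because the documents give no discharge distribution or post-discharge risk. With 30-60% discharged early and 0.5-5% risk, about 0.3-6 events per 200 are missed. The main scenarios give a false difference of roughly 0.1-0.6 points. The upper risk is hard to credit at a 5% incidence, since it would place 2.5-3.0 of the 5 points after discharge when 50-60% leave early.

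It would be wrong to infer that a Stage II advantage would be produced by this rule. The direction is not fixed, and the likely bias is small against sampling error at 200 per stage. It matters most if incidence is near 5% and early discharge differs strongly between stages. It should be corrected because the correction is cheap, not because it threatens the study.

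**What to change.** 1. Reconcile Protocol 3.1.2, 3.3 and 3.4.1 so that the endpoint window and the recording window agree.
2. In Protocol 3.4.1 and SAP 6.1.1, for any patient readmitted to the site by PSHA + 7 days, use the existing 30-day review in both stages to abstract the pneumonia criteria, ventilation or support above the endpoint thresholds, and ICU or elevated care. Set the PPC flags from these.
3. State whether ICU admission on a hospital readmission counts towards the ICU component.
4. Report the in-hospital-only proportion alongside, and the percentage discharged before day 7 by stage.
5. If steps 2 and 3 are not taken, label the endpoint as in-hospital PPC to discharge or day 7, whichever comes first, and still report early discharge by stage.

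The cost is a few extra fields for the few patients readmitted within the window, taken from records that the sites already open, with no new visits. Once site readmissions are captured, the part of the false difference that they cause disappears. Care at other hospitals stays uncaptured in both stages, as now, and the report should say so.
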